C.6.j. Analysis: We will conduct an intention-to-treat analysis. The patient will be the unit of analysis. We will examine baseline characteristics of parents in control and intervention arms using Pearson's χ^2 tests (or Fisher's exact tests) for categorical variables and t-tests for continuous variables to assess for any unbalanced confounders. Any unbalanced confounders will be controlled for as covariates in all subsequent regression analyses. We will also compare baseline characteristics between parents with and without missing data. We will apply sensitivity analysis and multiple imputations techniques to address missing data.

Given the nested structure of the data, we will apply mixed effects regression models to examine the effects of the intervention on our primary outcome while controlling for covariates and accounting for correlations due to clustering. Let y_{ijk} denote the percent days under-immunized for child k who receives care from provider j at clinic i , let T_{ijk} be the intervention indicator (0=control, 1=intervention) for the child, let X_{ijk} be the collection of covariates that includes potential confounders (at patient, provider, or practice levels), then a mixed model that accounts for this specific nesting data structure can be specified by

$$y_{ijk} = T_{ijk}\alpha + X_{ijk}\beta + Z_{ijk}^{(3)} u_i^{(3)} + Z_{ijk}^{(2)} u_{ij}^{(2)} + \epsilon_{ijk}, \quad (1)$$

for $k = 1, \dots, n_{ij}$ first-level observations (patient) nested within $j = 1, \dots, M_i$ second level groups (provider), which are nested within $i = 1, \dots, M$ third-level groups (practices). $Z_{ijk}^{(3)}$ and $Z_{ijk}^{(2)}$ are design matrices for the third- and second-level random effects. Further normality and independence assumptions will be placed on random effects and error terms if the outcome is continuous. The above model specification represents a multi-level linear mixed model. Parameter estimates will be obtained through restricted maximum likelihood estimation. Robust sandwich standard error estimates to account for the clustering will be used for inference. In the above model specification, the parameter α captures the expected difference between intervention and control arms and will be our focus of inference. For binary outcomes, the above model specification can be adapted to mixed effects logistic regression with similar estimation and inference techniques.¹¹⁸

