For our fidelity study (Aim 2a), we will use conversation analysis (CA) to analyze use of the presumptive format to initiate the vaccine recommendation in videotaped data and the Motivational Interviewing Treatment Integrity (MITI) 4 system¹¹⁹ to assess MI fidelity. CA is the same analytic technique we have used in our preliminary work (see C.1.c.) and searches for patterns in the provider-parent interaction in which a behavior is systematically used to accomplish a social action either vocally or nonvocally.¹²⁰ MITI utilizes a 5-point Likert type scale to assess four MI dimensions (cultivating change talk, softening sustain talk, partnership, and empathy) and tallies 10 specific practitioner behaviors (questions, reflection, persuade with permission, giving information, affirm, emphasize autonomy, seek collaboration, persuade and confront). Summary scores include: (1) reflection to question ratio, (2) percentage of complex to simple reflections, and (3) percent of MI adherent statements.

[name] will utilize a subset of the videotaped encounters to develop a coding scheme for the PIVOT with MI communication practices. [name] and [name] will teleconference weekly with [name] during this analysis to review identified communication patterns and their correlation to the PIVOT with MI intervention. After completion of the coding scheme, [name] will then train multiple coders from the study team on the coding scheme using 10% of the videotaped data. We will measure inter-rater reliability between the coders using up to an additional 20% of the data until κ scores reach a minimum of .70. Coders will then continue to independently code all remaining data (and recode the initial 10% of training data). All discrepancies in coding between the coders will be resolved through discussion with [name].

C.6.k. Sample Sizes/Power Calculations: Based on preliminary data (see C.1.a.), children of VHPs had a mean percentage of days under-immunized of 26.2% (standard deviation [SD] 29.8) from birth to 19 months of

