age for 6 vaccines combined (Hepatitis B, DTaP, Hib, IPV, MMR, and Varicella).¹⁸ This corresponds to an average of 37 days late per vaccine dose. To be able to detect with adequate power ($\geq 90\%$) a decrease in under-immunization of 10 days—a decrease that has the potential to be clinically meaningful since 27 days would not be considered late for most vaccines because of the 30 day window in which most vaccine doses are recommended¹²¹—we need to enroll 600 VHP/newborn pairs total, with 300 per arm and 25 at each of the 24 study practices (assuming an α of 0.05, a SD of 20, and an intraclass correlation coefficient for within-clinic correlation of 0.02²⁸). Assuming a 10% prevalence of VHPs (see C.1.b),²⁸ we will need to approach 6,000 parents to reach our sample size goal. This is feasible to achieve in our designated 18 month recruitment period given our design to integrate PACV-SF screening of parents of newborns into standard practice workflow and our estimate (determined by spot chart reviews at PSPRN and COCONet practices) that there are ≥ 10 newborns per clinic per week in PSPRN and COCONet practices. If we vary our assumptions regarding VHP prevalence (7.5%) or SD (25), we would need to approach 8,000 and 12,000 parents, respectively, for adequate ($\geq 90\%$) power to detect the same effect size, both of which remain feasible within the 18 month enrollment period assuming ≥ 10 newborns per clinic per week. If we have unbalanced enrollment across study arms (i.e. not 1:1 enrollment in intervention and control arms), we will continue enrollment beyond 600 VHP/newborn pairs total in order to reach at least 300 VHP/newborn pairs per arm given the impact of an imbalance on our power.

For our fidelity outcome (Aim 2a), power can be considered in terms of the number of videotaped interactions needed to develop this coding scheme. Based on our prior studies (see C.1.c.), 3 videotaped visits per provider should be adequate to achieve sufficient behavioral variation across providers. We will therefore videotape up to 360 encounters (up to 180 in each state), which averages to 3 videotaped encounters per practice provider.

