visit if the parent gave their contact information on the PACV survey and agreed to be contacted to potentially participate in future research. A RA will call and contact the parent to gauge interest in the survey and if so, will proceed with administering the survey either via an emailed link or over the phone, while the RA will enter their answers in real time in REDCap. Once the survey is completed, the parent will receive a \$20 gift card as a thank you.

To assess provider time, communication approach, and self-efficacy in discussing vaccines with parents, we will administer surveys to all study providers at baseline, after the completion of the trainings in the intervention practices and at study completion. Baseline surveys will also include items querying provider demographic and practice characteristics. The survey instrument will be modified from a survey used in the PCOM project (see *C.1.d.*) and pilot tested (Appendix 3). The interim and post study surveys will have the same questions for both intervention and control providers, with a few additional questions evaluating the PIVOT with MI trainings and experiences among intervention providers only. Administration will be by paper or electronically, depending on practice preference. Participants will receive a \$25 gift card for participation. In previous studies with similar methods, we've achieved 87-95% provider response rates.

An additional survey taken by each of our pediatric clinics will better help us understand the impact of COVID-19 on health supervision visits and vaccine delivery and uptake. This survey will be administered in the summer months of 2020.

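### The plan accepts that COVID-19 affects infant vaccination, but the primary model pre-specifies no birth-timing covariate; the main cost is precision and exposure to chance imbalance

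*Combined protocol and SAP*

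**What the plan says.** **COVID-19.** Aim 3 and C.7.c accept that the pandemic may have changed how infant vaccines were delivered and taken up. C.7.c adds a survey of clinics, in summer 2020, on the "impact of COVID-19 on health supervision visits and vaccine delivery and uptake". It also separates the parent-experience survey from the in-person visit. No link from either change to the primary analysis is described.

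**Outcome.** C.6.i defines the primary outcome as the percentage of days under-immunized from birth to 19 months over 22 doses.

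**Model.** C.6.j fits a linear mixed model with arm, covariates X, and random effects for practice and provider, using robust standard errors. X is said to "be the collection of covariates that includes potential confounders (at patient, provider, or practice levels"). The only stated selection rule is to compare parents' baseline characteristics between arms and adjust for those found unbalanced. No calendar or birth-date term is named there, among the survey's demographic items (C.6.g), or among the four variables balanced at randomization (C.6.e).

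**Accrual.** Randomization is run separately in Colorado and Washington (C.6.e). The intervention period starts when baseline training ends, and each intervention practice has its own session (C.6.f). If the arms fill unevenly, C.6.k says "we will continue enrollment beyond 600 VHP/newborn pairs total in order to reach at least 300 VHP/newborn pairs per arm"; it gives no closing date.

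**The concern.** A child's outcome depends on how much of the 19-month window fell in the disrupted period. The plan therefore acknowledges a factor likely to be prognostic and leaves its use to a test for baseline imbalance that, as described, covers parent characteristics only. Whether a covariate tests as unbalanced is a poor reason for including or omitting it. A prognostic variable earns its place through the outcome variance it explains, and adjusting for it removes whatever chance imbalance has occurred.

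At stake are some precision in the arm comparison, an estimate that can be shifted by uneven exposure across a modest number of practices, and a decision about pandemic adjustment that would otherwise be made after data are available.

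**Working it through.** **1. The plan's own figure.** Inputs from C.6.k: 600 pairs, 300 per arm, 25 in each of 24 practices, SD 20, ICC 0.02, alpha 0.05 (taken as two-sided), and "a decrease in under-immunization of 10 days". The reference mean of 26.2% is equated with 37 days late per dose. SD 20 is read as percentage points.

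- Target: 10/37 × 26.2 = 7.08 points.
- Design effect: 1 + (25 − 1) × 0.02 = 1.48.
- SE of the arm difference: 20 × √(2 × 1.48/300) = 1.99 points.
- Power: Φ(7.08/1.99 − 1.96) = 94.6%, or 92.6% using a t reference with 22 df.

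This meets the stated 90%. The sample size is not in question here.

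**2. Precision lost by omitting birth period.** Assumptions: half of births are affected, and the shift in mean outcome is 5 to 15 points. Variance explained = 0.5 × 0.5 × shift²/SD². The SDs are the planning value of 20 and the preliminary 29.8 from C.6.k.

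| Shift (points) | SD 20 | SD 29.8 |
|---|---|---|
| 5 | 6.25/400 = 1.6% | 6.25/888 = 0.7% |
| 15 | 56.25/400 = 14.1% | 56.25/888 = 6.3% |

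The range is about 1% to 14%. At the top, adjustment would shrink the SE by 1 − √(1 − 0.141) = 7%, if the term explains the same share of variance within and between practices.

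**3. Chance imbalance.** Suppose the share of affected births varies between practices with SD s of 10 to 20 points (assumed). With 12 practices per arm, the arm difference in share has SE s × √(2/12), which is 4.1 to 8.2 points. Multiplied by shifts of 5 to 15 points, a one-SE imbalance moves the estimate by 0.2 points (0.041 × 5) to 1.2 points (0.082 × 15), against the SE of 1.99. The lower s needs no real difference between practices: 25 children with half affected give √(0.25/25) = 10 points from sampling alone.

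**4. Bias if accrual did differ by arm.** Bias = difference in affected share × shift. Differences of 5 to 15 points with shifts of 5 to 15 points give 0.05 × 5 = 0.25 to 0.15 × 15 = 2.25 points, or 4% to 32% of 7.08. Both factors are assumed.

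**5. Price of adjusting.** If affected shares differ between arms by d around 50%, the correlation between arm and period is d, and the variance of the arm effect is inflated by 1/(1 − d²). The figures below credit no gain from step 2.

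| d | Inflation | Power (normal) | Power (t, 22 df) |
|---|---|---|---|
| 0.10 | 1.01 | 94.4% | 92.3% |
| 0.20 | 1.04 | 93.7% | 91.6% |
| 0.30 | 1.10 | 92.5% | 90.1% |

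**The case against.** A reader might infer that the trial confounds arm with the pandemic. The strongest reply has four parts.

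- **Chance imbalance is not bias.** Under randomization, uneven exposure between practices is variance, and the practice random effects and robust standard errors largely carry it. This stands. What remains is lost precision and an estimate shifted by the imbalance actually realized.
- **The design already limits the problem.** Separate randomization by state balances state-specific pandemic timing. Provider numbers and the percentage of hesitant parents, both plausible drivers of accrual speed, are constrained. This also stands.
- **The extension does not imply that one arm closes at 300.** A reader might picture the faster arm stopping while the slower one recruits later births. If that happened, the total would end at exactly 600. Enrolment going beyond 600 in order to reach 300 in each arm implies that the leading arm passes 300. The text is silent only on whether that arm later closes before the other finishes.
- **Birth date is unnamed, not excluded.** X is open to any patient-level confounder. That is true, but the stated rule for filling X looks at parent characteristics, so an acknowledged influence on the outcome would enter only by later discretion.

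The magnitudes are also assumed throughout. A shift of 5 to 15 points is 19% to 57% of the 26.2% reference mean, and treating each birth as disrupted or not is crude when many 19-month windows could be partly exposed.

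**Conclusion.** The point holds as a gap in covariate pre-specification. The plan recognises the pandemic's effect on infant vaccination, and its primary model makes no provision for it. With practices randomized within state and enrolling concurrently, exposure should be similar between arms on average. The expected cost is about 1% to 14% of outcome variance left unexplained, plus chance shifts of roughly 0.2 to 1.2 points for a one-SE imbalance. These figures assume a 5 to 15 point pandemic shift, half of births affected, and practice shares varying with SD 10 to 20 points. The documents supply none of these values.

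The documents do not support a finding of systematic bias. That would require calendar accrual to differ by arm, for example through start dates tied to training in intervention practices only, or an arm closing early during the extension. They give no accrual by arm and no enrolment dates, so the 0.25 to 2.25 point range is conditional on that happening. The change is still worth making because it costs almost nothing.

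**What to change.** In C.6.j, add one birth-timing covariate to Equation (1), with a state interaction, and include it regardless of any imbalance test. Choose one form in advance: either the number of days of the 0 to 19 month window that fall after pandemic onset, or a small number of birth-cohort categories. Define the onset date in the SAP. Quarter of birth by state over 18 months would give about 12 cells (6 quarters × 2 states), so a coarser form is preferable.

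The cost is SAP wording and a few degrees of freedom at the child level. Date of birth is already needed to compute the outcome, and the sample size stays at 600. Power stays above 90% under the planning assumptions, even with a 30-point difference between arms in affected share.

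As a minor clarification to C.6.k, state that both arms remain open until a common closing date in any extension beyond 600.

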C.6.e. Covariate-constrained Randomization: Practices will be the unit of randomization. A key issue in cluster-randomized trials is the possibility of covariate imbalance in practices assigned to different treatment arms.¹⁰⁴⁻¹⁰⁸ Thus, practices will be randomly assigned to assure balanced comparison groups using optimized probability sampling to the intervention or control arm in the following manner. From the pool of practices that agree to participate in the study, pre-study information will be collected on several characteristics that may influence study outcomes: percent of VHPs, percent of Vaccines-for-Children [VFC]-eligible patients, number of pediatric providers, and practice immunization rates of children 19-35 months old. These pre-study variables will then be used to develop and evaluate a balance criterion, defined as the sum of the squared differences between standardized practice means on these variables.¹⁰⁵ All possible combinations of eligible practices in 2 arms (intervention and control) will be generated using a SAS macro program.¹⁰⁷ The distribution of the balance criterion for the 2 study arms will be used to define an acceptable set of study arms that are reasonably balanced in terms of the selected variables (minimum 10% of balance criterion).¹⁰⁵ From this set, one set will be chosen at random and used to randomly assign each practice to intervention or control arms. This process will be undertaken in both Colorado and Washington as separate randomization procedures. We have successfully used covariate-constrained randomization in C.1.d. and other studies.^{109,110}

We will perform the following procedures to obtain pre-study information on these covariates:

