At the conclusion of the video module window, providers will be asked to attend a 90 minute interactive in-person training session led by study staff. Attendance will be required for MOC Part 4 credit. This baseline training session will involve a baseline assessment of provider skills with the communication techniques introduced in the module and teaching and reinforcement of the PIVOT with MI strategy using modeling, role-playing and coaching by the study team. Providers will also receive instructions on how to use the reference sheets developed in Aim 1. Each intervention practice will have its own in-person training session. For PSPRN practices, sessions will be led by [name], [name], [name], and [name]. For COCONet practices, sessions will be led by [name], [name], and [name]. Based on our previous work, provider participation rate in this baseline training is expected to be $\geq 70\%$ (see *C.1.b.* and *C.1.d.*). The intervention period will commence at the conclusion of this baseline training and last 36 months (constituting the 18 month parent recruitment period [see *C.6.k.*] and the 18 months after this period to allow for the last enrolled newborn to reach 19 months old).

Six months into the intervention period, providers will receive a 60 minute in-person refresher training led by the same study team members. This will take a similar format to the initial training but will start with providers sharing their experiences with the PIVOT with MI intervention over the prior 6 months, with demonstrations from each provider of a difficult vaccine conversation with feedback from the MI trainer. At 12 months into the intervention period, we will have a second 90 minute in-person refresher training that will also include viewing 3-5 selected videotaped encounters of 2, 4 and/or 6 month health supervision visits involving intervention providers (with their permission) from the preceding 12 months (see *C.6.g.*) to illustrate “dos and don’ts” of the PIVOT with MI strategy. We will ask providers at the refresher training what they thought went well and what could be improved after watching each videotape. Study champions (1 per practice) will support the PIVOT with MI strategy throughout the remainder of the intervention period by soliciting periodic feedback from providers on use of the intervention and addressing implementation issues with the study team.

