C.7.d. Analysis: Since there is no optimal method for summarizing parent experience, we will use 2 dichotomization methods: the top-box method,¹²⁵⁻¹²⁸ consistent with Consumer Assessment of Healthcare Providers and Systems survey scoring,¹²⁹ and an alternative method^{123,130,131} in which an average score of ≥ 6 (out of 7) on each of the 15 items is indicative of a highly rated visit experience.¹⁶ We will also summarize parent experience as a continuous variable. We will use Pearson's χ^2 test to compare parent (binary) ratings of visit experience between control and intervention arms. We will apply mixed effects logistic regression model to account for within-clinic correlation and any unbalanced confounding factors. When summarizing parent experience as a continuous variable, we will apply Box-Cox transformation if it is highly skewed and linear mixed effect models similar to Equation (1) to examine differences between control and intervention arms.

For the provider outcomes, we will compare the pre- and post-intervention proportions of control and intervention providers who (1) spent <10 minutes vs. 10+ minutes discussing vaccines at a typical visit and during visits with parents who had vaccine concerns; (2) used the presumptive and/or MI techniques in vaccine discussions with families (always, frequently, sometimes, never); and (3) perceived they were able to influence parents' vaccine decisions (Appendix 3). We will use Pearson's χ^2 test for an unadjusted analysis of the pre-post differences between control and intervention arms and multivariable logistic regression for adjusted analyses that control for potential confounding variables such as provider demographic and practice characteristics. Planned subgroup analyses include examining outcomes by practice type (public/private), %VHPs in the practice, and number of practice providers. Models will account for clustering of outcomes by practices where needed.

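### Section C.7.d does not say how the provider analysis uses each provider's repeated answers, and it makes practice clustering conditional; one prespecified linked, clustered model should replace the tests named there

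*Combined protocol and SAP*

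**What the plan says.** **Measurement.** Section C.7.c states that "we will administer surveys to all study providers at baseline, after the completion of the trainings in the intervention practices and at study completion". Pre and post answers therefore come largely from the same people, and there are three survey waves. No linkage of a provider's surveys is described.

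**Tests.** C.7.d compares pre- and post-intervention proportions for time spent, use of the techniques and perceived influence on parents' decisions. It names Pearson's chi-square test for an "unadjusted analysis of the pre-post differences between control and intervention arms and multivariable logistic regression for adjusted analyses". The adjusted analyses are to "control for potential confounding variables such as provider demographic and practice characteristics". The interim survey is given no role in this comparison.

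**Clustering.** C.7.d adds: "Models will account for clustering of outcomes by practices where needed". It gives no criterion and no method, and the sentence covers models, not the chi-square test. Section C.6.e states "Practices will be the unit of randomization", and section C.6.f states "Each intervention practice will have its own in-person training session".

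**Contrast.** For parent visit experience, the same section follows its chi-square test with a mixed effects logistic model for within-clinic correlation, without any such condition.

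**The concern.** Two features of the data should shape the provider analysis. A provider's answers at different waves are correlated, and the arms differ by practice, not by provider. A Pearson chi-square test on counts of answers uses neither fact. The named covariates do not include the provider's earlier answer to the same question, which is likely to be the best predictor of the later one and is already collected.

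These tests decide the provider hypotheses of Aim 3 (less time and better self-efficacy in vaccine discussions). With about 60 providers per arm there is little precision to spare. Leaving the analysis open also leaves a choice, after the data are seen, between methods with very different error rates.

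**Working it through.** **Inputs from the documents.** Control change +1 point, intervention change +13 points, 60 providers per arm, 80% power, 5-7 providers per practice (C.7.e); alpha 0.05 and ICC 0.02, both stated for the primary outcome only (C.6.k); 24 practices (C.6.a).

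**Assumptions.** The documents give no baseline proportion, no within-provider correlation r and no ICC for provider outcomes. I take baselines of 10% and 50%, r from 0.3 to 0.7, ICC from 0.02 to 0.10, and two-sided testing.

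**Step 1: the plan's own figure.** Treat 1% and 13% as two independent simple proportions with 60 per arm and apply the uncorrected Pearson chi-square test. Exact enumeration gives 80.8% power, against the stated 80%. The figure is therefore matched by treating each arm's net change as one binomial proportion, with no baseline variance, no pairing and no clustering.

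**Step 2: pre and post compared as independent proportions.** With similar proportions at the two waves, the variance of a provider's change is (1 - r) times its value under independence. The standard error is therefore too large by 1/sqrt(1 - r), and the true alpha is 2 × [1 - Φ(1.96/sqrt(1 - r))].

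| r | SE ratio | true alpha |
|---|---|---|
| 0.3 | 1.20 | 1.9% |
| 0.5 | 1.41 | 0.6% |
| 0.7 | 1.83 | 0.03% |

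Simulation under the null (24 practices of 5 providers, 50% baseline) agrees in direction: 1.5% error at a latent correlation of 0.5, and 5.3% once standard errors are clustered by provider. Adding a time-stable practice effect (latent ICC 0.05) leaves the unpaired error at 1.7%, because such an effect largely cancels in a pre-post contrast.

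**Step 3: power at the plan's effect, no clustering.** At a 50% baseline the proportions are 0.50 to 0.51 (control) and 0.50 to 0.63 (intervention).
- Independent SE = sqrt[(0.25 + 0.2499 + 0.25 + 0.2331)/60] = 0.128.
- Paired SE at r = 0.5 = 0.0905.
- Baseline-adjusted SE = 0.128 × sqrt[(1 - 0.5²)/2] = 0.0784.
- Unpaired test: Φ[(0.12 - 1.96 × 0.128)/0.0905] = 7%.
- Paired: Φ(0.12/0.0905 - 1.96) = 26%.
- Baseline-adjusted: Φ(0.12/0.0784 - 1.96) = 33%.

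| baseline | r | unpaired | paired | baseline-adjusted |
|---|---|---|---|---|
| 50% | 0.3 | 11% | 20% | 28% |
| 50% | 0.5 | 7% | 26% | 33% |
| 50% | 0.7 | 3% | 40% | 46% |
| 10% | 0.5 | 21% | 48% | 61% |

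**Step 4: post answers only, no clustering.** Design effect DE = 1 + (m - 1) × ICC; true alpha = 2 × [1 - Φ(1.96/sqrt(DE))], for m = 5 to 7.

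| ICC | DE | true alpha |
|---|---|---|
| 0.02 | 1.08-1.12 | 5.9-6.4% |
| 0.05 | 1.20-1.30 | 7.4-8.6% |
| 0.10 | 1.40-1.60 | 9.8-12.1% |

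Steps 2 and 4 describe different analyses. They do not add up, and they cannot be relied on to cancel.

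**The case against.** The strongest reply is that the plan is terse, not mistaken. The chi-square is applied to pre-post differences, which may mean one change result per provider compared between arms; the power figure in C.7.e fits that reading. The unpaired standard error of Step 2 then does not arise. The regression outcome is not fixed, and the covariate list is introduced as examples ("control for potential confounding variables such as provider demographic and practice characteristics"), so the baseline answer is not excluded. Clustering is mentioned for the models. The alpha of 10-12% needs an ICC five times the only one in the documents and a post-only comparison that C.7.d does not clearly plan.

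Much of this stands. A reader might infer that the provider p-values are certain to be wrong, and in both directions. The text does not support that, because the conservative and liberal errors belong to different readings. Nor does it support saying that most of the baseline information is lost: the share of variance forgone by not pairing is about r, so 'most' needs r above 0.5, and no r is given. For parents, an unadjusted chi-square stands beside a clustered model, so that outcome is not left without a valid test.

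What the reply does not remove is the open choice. Even on the change-per-provider reading, a two-category change such as improved or not merges providers who worsened with those who already gave the favourable answer. No reading of C.7.d makes clustering unconditional, although the practice is the randomised unit.

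**Conclusion.** The point holds as an under-specified analysis for which a better method is available at almost no cost. The wording admits analyses whose true alpha runs from well below 1% to about 12%, depending on the reading and on assumed r and ICC. At the plan's 12-point difference, using the linked baseline answer raises power from about 7% to 33% at a 50% baseline and r = 0.5, and from about 21% to 61% at a 10% baseline and the same r. These are normal approximations without clustering or survey non-response; they show the relative merit of the methods and do not predict the trial's power.

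Only the secondary provider outcomes of Aim 3 are at issue. A reader might extend the criticism to the primary outcome, but the model in C.6.j already nests children within providers within practices.

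**What to change.** In C.7.d:

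- State that each provider's baseline, interim and completion surveys are linked by a study ID.
- For each provider outcome prespecify one model. Either regress the post answer on arm, adjusted for the provider's baseline answer; or fit a repeated-measures logistic model with arm, time (baseline, interim, completion) and arm-by-time, allowing for within-provider correlation. The second gives the interim survey a role and keeps providers with incomplete surveys. This matters: at the 87-95% response quoted in C.7.c, and if non-response is independent between waves, 60 providers yield only 60 × 0.87² = 45 to 60 × 0.95² = 54 complete pre-post pairs per arm.
- Always include practice clustering, with a small-sample correction for 24 practices, and delete 'where needed'.
- Make the chi-square tests descriptive only. For parent visit experience, name the mixed logistic model already planned as the inferential test.

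The provider power statement in C.7.e should then be restated for the chosen model, with its baseline proportion, r and ICC given.

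The cost is analysis-plan wording and a linking ID on the surveys. No new data are needed.
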